### **6.5.1.2. HIV Treatment Satisfaction Change (HIVTSQc)**

HIVTSQc is to be completed by the participant at Week 4 (see [Table 3](#)). Participant is to read questionnaire by himself/herself and write/mark answers directly onto questionnaire. See [Appendix 11.4.1](#) for questionnaire.

### **6.5.1.3. Additional Study-Specific Questions**

A study-specific questionnaire will be completed by the participant on Day 1 and Week 4 to document preference for oral vs injection therapy and specific reasons for decisions to switch from CAB+RPV to oral therapy. Refer to [Appendix 11.4.3](#) for study-specific questionnaire.

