## 2. OBJECTIVES AND ENDPOINTS

Primary Objective	Co-Primary Endpoints

To assess the safety of switching to B/F/TAF in virologically suppressed participants unable/unwilling to continue on CAB+RPV IM injections or wishing to switch to oral therapy through Week 12

	

Proportion of participants experiencing treatment-emergent Grade 3 or 4 study drug-related adverse events through Week 12

Proportion of participants experiencing treatment-emergent Grade 3 or 4 laboratory abnormalities through Week 12

Secondary Objectives	Secondary Endpoints

To assess the pharmacokinetics of BIC, CAB, and RPV after switching to B/F/TAF from CAB+RPV

To assess the efficacy and persistence of B/F/TAF after switching from CAB+RPV

To assess the safety of B/F/TAF after switching from CAB+RPV through Week 24

To evaluate treatment satisfaction of switching to B/F/TAF from CAB+RPV

	

Plasma concentrations of BIC, CAB, and RPV at Day 1, Weeks 4, 12, and 24, as appropriate

Proportion of participants with HIV-1 RNA <math>\geq 50</math> copies/mL at Weeks 12 and 24 (missing = excluded and discontinuation = failure)

Number and proportion of participants with B/F/TAF discontinuation by Weeks 12 and 24

Proportion of participants experiencing treatment-emergent grade 3 or 4 laboratory abnormalities through Week 24

Change in HIV treatment satisfaction (HIVTSQc) score at Week 4

Exploratory Objective	Exploratory Endpoints

To understand PWH experience with injectable and oral therapies for HIV treatment

To evaluate reasons for switching to B/F/TAF from CAB+RPV

	

Participant reported experiences with CAB+RPV, preferences for injectable and oral therapies

Participant-reported reasons for switching to B/F/TAF

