### 3. STUDY DESIGN

#### 3.1. Study Design Overview

This study is a Phase 4, single-arm, open-label, multicenter interventional switch study to evaluate the safety, PK, and efficacy of daily oral B/F/TAF 50/200/25 mg in virologically suppressed adults with HIV-1 infection who are unable/unwilling to continue on CAB+RPV IM injections or wishing to switch to oral therapy. A total of approximately 35 participants (with at least 20 participants with evaluable PK) will be enrolled in the study including approximately 10 participants in France; French participants will not undergo PK analysis and qualitative interview.

[figure not shown]
This study will evaluate the PK of BIC and residual levels of CAB and RPV following initiation of B/F/TAF 50/200/25 mg once daily by means of sparse PK sampling.

The study will enroll male and nonpregnant, nonlactating female PWH  $\geq$  18 years of age.

An overview of the study design is described in [Figure 1](#). Participants in North America will have safety, efficacy, and sparse PK assessments, receive quantitative questionnaires, and be eligible for qualitative interviews, while participants in France will have safety and efficacy assessments and receive quantitative questionnaires.

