### **6.5.1.4. Qualitative Interviews (English only)**

Among the participants who are recruited and consented to undergo qualitative interviews, a vendor will schedule face to face (or telephone) interviews with these participants in English over a video communication platform. Interviews will cover topics such as reasons for switching to B/F/TAF; experiences using CAB+RPV, including injection site reactions, side effects, time spent via clinic visits, etc; preferences for injectable and oral HIV medications; and treatment satisfaction post switch. Interviews will be recorded and transcribed for data analysis purposes. The qualitative interview will occur near the Week 4 visit (visit window range Week 3-9). Refer to [Appendix 11.4.2](#) for qualitative interview guide.

The qualitative interviewer would be responsible for notifying the investigator of all the AE's/SAE's/SSR's identified during the interview within 24 hours of awareness. Please refer to [Section 7.4](#) for the reporting process.

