**10. How much did the side effects experienced while on CAB + RPV (Cabenuva) bother you?**

	Please check the one best answer
They don't bother me at all	 (a)
I am a little bothered by them	 (b)
I am moderately bothered by them	 (c)
I am very bothered by them	 (d)
I am extremely bothered by them	 (e)

Participant ID Number: \_\_\_\_\_ Date of Survey: (month/day/year) \_\_\_\_\_

11. Why did you decide to switch from CAB + RPV (Cabenuva) to daily oral medication B/F/TAF (Biktarvy)?

*Please check all answers that apply*

I didn't like the side effects of CAB + RPV (Cabenuva)	 (a)
Visits to the clinic were too frequent	 (b)
Waiting time in the office to get injections	 (c)
Difficulty with insurance or cost	 (d)
Difficulty scheduling appointments for injections	 (e)
I want to have less in-person contact with the healthcare system	 (f)
I have anxiety about receiving injections	 (g)
I prefer oral medication over injections	 (h)
A doctor, nurse, social worker or other health practitioner said I should switch	 (i)
A friend, relative, partner, acquaintance or other patient said I should switch	 (j)
I already take on other daily oral medication, so taking one more wouldn't make a difference	 (k)
Concern that the medication in the injection might not last 2 months	 (l)
Concern about developing resistance with CAB + RPV (Cabenuva)	 (m)
I want to be in more control of my HIV medication	 (n)
I took B/F/TAF (Biktarvy) before and I had a good experience with it	 (o)
I think B/F/TAF (Biktarvy) is more effective than CAB + RPV (Cabenuva)	 (p)
I think B/F/TAF (Biktarvy) has less side effects than CAB + RPV (Cabenuva)	 (q)
Another reason (please describe in the box below)	 (y)

→ DESCRIBE BELOW

*If you selected "Another reason", please describe that here:*

Participant ID Number: \_\_\_\_\_ Date of Survey: (month/day/year) \_\_\_\_\_

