12. Of all the reasons you checked in question 10, which would you rank as the TOP reason you decided to switch from CAB + RPV (**Cabenuva**) to daily oral medication B/F/TAF (Biktarvy)?

*Please check the  
one best answer*

I didn't like the side effects	 (a)
Visits to the clinic were too frequent	 (b)
Waiting time in the office to get injections	 (c)
Difficulty with insurance or cost	 (d)
Difficulty scheduling appointments for injections	 (e)
I want to have less in-person contact with the healthcare system	 (f)
I have anxiety about receiving injections	 (g)
I prefer oral medication over injections	 (h)
A doctor, nurse, social worker or other health practitioner said I should switch	 (i)
A friend, relative, partner, acquaintance or other patient said I should switch	 (j)
I already take on other daily oral medication, so taking one more wouldn't make a difference	 (k)
Concern that the medication in the injection might not last 2 months	 (l)
Concern about developing resistance with CAB + RPV (Cabenuva)	 (m)
I want to be in more control of my HIV medication	 (n)
I took B/F/TAF (Biktarvy) before and I had a good experience with it	 (o)
I think B/F/TAF (Biktarvy) is more effective than CAB + RPV (Cabenuva)	 (p)
I think B/F/TAF (Biktarvy) has less side effects than CAB + RPV (Cabenuva)	 (q)
Another reason ( described in the box below Question 10 )	 (y)

13. How hopeful do you feel about starting Biktarvy in terms of successfully treating your HIV?

*Please check the  
one best answer*

Very hopeful	 (a)
Hopeful	 (b)
Somewhat hopeful	 (c)

Participant ID Number: \_\_\_\_\_ Date of Survey: (month/day/year) \_\_\_\_\_

Not hopeful at all	 (d)
--------------------	---------------------------

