3.7.2. Analysis Visit Windows

Participant visits might not occur on protocol-specified days. Therefore, for the purpose of analysis, observations will be assigned to analysis windows for all analysis except PK analysis.

The analysis windows for Plasma HIV-1 RNA, Hematology, Chemistry, Urinalysis and Urine Pregnancy Laboratory Tests, Vital Signs and Weight are provided in Table 3-1.

The analysis windows for CD4+ cell count, CD4 %, estimated GFR_{CG} (Estimated GFR according to the Cockcroft-Gault formula for creatinine Clearance), and Metabolic Assessments (including fasting glucose and lipid panel: total cholesterol, high density lipoprotein [HDL], direct low density lipoprotein [LDL], triglycerides, and total cholesterol to HDL ratio) are provided in Table 3-2.

Analysis windows for the HIVTSQs are provided in Table 3-3.

HIVTSQc and Qualitative Interviews (English only) are to be completed by the participant at Week 4 with analysis window shown in Table 3-4.

A study-specific questionnaire will be completed by the participant on Day 1 (Baseline) and Week 4 with analysis window shown in Table 3-5.

Table 3-1. Analysis Visit Windows for Plasma HIV-1 RNA, Hematology, Chemistry, Urinalysis and Urine Pregnancy Laboratory Tests, Vital Signs and Weight

Visit	Study Day	Visit Window Study Day	
		Lower Limit	Upper Limit
Baseline	1	(none)	1
Week 4	28	2	56
Week 12	84	57	126
Week 24	168	127	210

Table 3-2. Analysis Visit Windows for CD4+ Cell Count, CD4 %, eGFR_{CG}, and Metabolic Assessments

Visit	Study Day	Visit Window Study Day	
		Lower Limit	Upper Limit
Baseline	1	(none)	1
Week 12	84	2	126
Week 24	168	127	210

Table 3-3. Analysis Visit Windows for HIVTSQs

Visit	Study Day	Visit Window Study Day	
		Lower Limit	Upper Limit
Baseline	1	(none)	1
Week 12	84	2	126
Week 24	168	127	210

Table 3-4. Analysis Visit Windows for HIVTSQc and Qualitative Interview

Visit	Study Day	Visit Window Study Day	
		Lower Limit	Upper Limit
Week 4	28	2	56

Table 3-5. Analysis Visit Windows for Additional Study Specific Questions

Visit	Study Day	Visit Window Study Day	
		Lower Limit	Upper Limit
Baseline		(none)	1
Week 4	28	2	56

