9.1. Patient-Reported Outcomes

The PRO related secondary endpoint include:

- Change in HIV treatment satisfaction (HIVTSQc) score at Week 4.

The PRO related other endpoint include:

- Total score and change from baseline in HIVTSQs at Week 12 and 24.

The PRO related exploratory endpoints include:

- Week 12 reported experiences with CAB+RPV, reasons for switch to B/F/TAF, preferences for injectable and oral therapy from qualitative interviews of participant experience
- Participant-reported perceptions of CAB+RPV treatment, reasons for switch to B/F/TAF.

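### The Day 1 and Week 4 survey does not ask which route participants prefer, and its Week 4 form, its top-reason item and the SAP's interview timing do not match the exploratory analyses planned from them

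*Protocol*

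**What the plan says.** - **Endpoints.** Protocol section 2 lists two exploratory endpoints. One is "Participant reported experiences with CAB+RPV, preferences for injectable and oral therapies"; the other is the participant's reasons for switching to B/F/TAF.
- **Survey purpose.** Protocol 6.5.1.3 gives a questionnaire at Day 1 and Week 4 "to document preference for oral vs injection therapy and specific reasons for decisions to switch from CAB+RPV to oral therapy". The forms are in Protocol Appendix 11.4.3.
- **Planned summaries.** Protocol 8.8.2 summarizes switch reasons by visit. SAP 9.2.2 plans proportions with specific reasons at Baseline and Week 4.
- **Top-reason item.** Day 1 Q12 in the protocol begins "Of all the reasons you checked in question 10", and its write-in option refers to a box below the same question. Question 10 reads "How much did the side effects experienced while on CAB + RPV (Cabenuva) bother you". SAP Appendix 4 prints Q12 with a pointer to question 11.
- **Interview.** Protocol 6.5.1.4 makes it subject to separate recruitment and consent, in English only, near Week 4 ("visit window range Week 3-9"). Protocol 3.1 states that "French participants will not undergo PK analysis and qualitative interview". Protocol 8.8.1 says only that the results may be explored.
- **Interview in the SAP.** SAP 3.7.2 states: "HIVTSQc and Qualitative Interviews (English only) are to be completed by the participant at Week 4 with analysis window shown in Table 3-4". That table gives nominal Day 28 and limits of Day 2 to Day 56. SAP 9.1 describes the interview endpoint as "Week 12 reported experiences with CAB+RPV".

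**The concern.** An instrument with a stated purpose should contain an item that serves it. Here the survey is meant to capture preference, and option (h) in Q11 is the only place where preference can show. A tick means that preferring tablets was a reason to switch. A blank could mean that the participant prefers injections, has no preference, or prefers tablets but did not switch for that reason. These are not idle possibilities. Inclusion criterion 2 admits switches decided by the provider or caused by intolerance, and Q11 itself offers insurance or cost and a practitioner's advice as reasons. Someone who would rather have stayed on injections can be in the study and has nowhere on the form to say so.

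The practical risk is that the percentage ticking (h) is reported as the percentage preferring oral therapy. A second risk is a Week 4 summary of switch reasons for which no data were collected. The faulty Q12 pointer and the interview timing are smaller, but they sit in the same component and need settling before it is reported.

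**Working it through.** No power calculation exists for this study, so the check is an item count, a cross-reference check and day arithmetic.

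**1. Survey content (Protocol Appendix 11.4.3)**
- Day 1, 13 items: direct preference items 0; switch-reason items 2 (Q11 and Q12). Option (h) is one of 18 answers in Q11: (a) to (q) is 17, plus (y).
- Week 4, 5 items: four on side effects and one on missed doses. Preference items 0; switch-reason items 0.
- Reasons can therefore be summarized at Day 1 only. A by-visit summary has an empty Week 4 column.

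**2. Who can supply preference data**
- Planned: about 35 participants, about 10 of them in France (Protocol 4.1).
- No interview by design: 10/35 = 28.6%.
- Upper limit for interviews: 35 − 10 = 25, and 25/35 = 71.4%. The actual share depends on consent and on English, and the documents give neither.
- French participants do complete HIVTSQs and HIVTSQc. HIVTSQc at Week 4 compares satisfaction with the previous and the current treatment, but does not ask which route is preferred.

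**3. Q12 pointer**
- Protocol Q10 measures how bothersome side effects were. Q8 sends participants without side effects straight to Q11, so they never see Q10.
- The reasons and the write-in box belong to Q11. Protocol Q12 points to 10 in both places; SAP Appendix 4 prints 11.

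**4. Interview window**
- The SAP sets nominal day = 7 × week: 7 × 4 = 28, 7 × 12 = 84, 7 × 24 = 168, all as stated.
- Its Day 56 limit is the midpoint between visits: (28 + 84)/2 = 56. The Week 12 limit follows the same rule: (84 + 168)/2 = 126. So Day 56 is a generic Week 4 limit and was not derived from the interview window.
- On that convention Week 3 is Day 21 and Week 9 is Day 63. Permitted days: 63 − 21 + 1 = 43. Days beyond the SAP limit: 63 − 56 = 7. Share: 7/43 = 16.3%.
- Other ways of counting weeks: Days 15 to 63 give 7/49 = 14.3%; Days 22 to 64 give 8/43 = 18.6%.
- These are shares of permitted calendar days, not of participants.

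**5. Timing label**
- Protocol 6.5.1.4, Protocol Table 3 and SAP 1.2.1 all place the interview at Weeks 3 to 9. The Week 12 label in SAP 9.1 matches none of them.

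**The case against.** The strongest reply is that the plan assigns preference to the interview, not to the survey. The heading of Protocol 8.8.1 and SAP 9.1 both say so. The interview takes place after the switch, and the guide covers the subject: Q4 asks about the ideal treatment and how it would be given, Q5 compares the two treatments, and Q15 and Q23 ask about comfort with how each is given. This stands. A reader might infer from the forms that the preference endpoint has no data after the switch; the documents do not support that. What remains is that Protocol 6.5.1.3 promises something the survey does not contain.

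Leaving France out of the interviews is a disclosed choice, so the 29% measures that choice and is not an error in itself. It matters because the survey would otherwise have been the French source for preference.

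On Q12, a reader might infer that the top reason cannot be answered. It can: the item follows Q11 and reprints the whole list. Because the two documents differ, the wording actually fielded is unknown. Switch reasons are also collected from everyone in Q11.

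On the window, a reader might infer that late interviews are discarded, or might apply 16% to 25 North American participants. Neither follows. SAP 3.3 lists no interview table and puts all available data in the listings, so an interview on Days 57 to 63 would lack an analysis visit but would not be lost. A count of participants would need even timing across the window and universal consent; the protocol says the interviews are held near Week 4 and are optional.

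Finally, SAP 2.1 and 2.1.1 describe the North American Week 12 interim as already done, so a new item may come too late for those participants. This stands, and it shapes the fix.

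**Conclusion.** The point holds as a minor one, confined to exploratory endpoints; no primary or secondary endpoint is touched.

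- The survey cannot deliver the preference half of its stated purpose at either visit, and at Week 4 it delivers neither half. Reasons for switching are deliverable at Day 1.
- Preference data rest on at most about 25 of 35 participants, through interviews whose analysis is optional. About 10 of 35 have only option (h), which is a switch reason and not a measure of preference.
- Protocol Q12 and SAP Appendix 4 contradict each other, and the protocol's pointer is the wrong one. The likely harm is confusion, not loss of the item.
- Table 3-4 leaves 7 of 43 permitted interview days (16%; 14% to 19% by counting convention) without an analysis visit, and the SAP 9.1 label is wrong.

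This assumes that the appendix forms are those fielded, that enrollment is close to the planned 35 with 10 in France, and that weeks are counted as the SAP counts them.

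**What to change.** 1. **Preference.** Add one item (oral / injectable / no preference) to any Day 1 and Week 4 forms still to be administered. If none remain, restate the endpoint as preference from North American interviews only, amend Protocol 6.5.1.3 to match, and report option (h) only as a reason for switching. If the item reaches only some participants, say which.
2. **Switch reasons.** Restrict the summary in Protocol 8.8.2 and SAP 9.2.2 to Day 1.
3. **Q12.** Correct both protocol pointers to question 11 and record which wording participants saw.
4. **Interview window.** Give the interview its own row in SAP Table 3-4 with an upper limit of at least Day 63 (Day 64 if Week 9 is counted as Day 1 plus 63 days). The HIVTSQc limits can stay as they are.
5. **Label.** Replace Week 12 in SAP 9.1 with the Week 3 to 9 interview.

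Items 2 to 5, and the restatement under item 1, are text changes that need no new data; the SAP changes can be made before it is finalized. The new item costs one question on an existing form and the usual approval of a revised form, and is worth that only where forms are still outstanding.

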### **6.5.1.4. Qualitative Interviews (English only)**

Among the participants who are recruited and consented to undergo qualitative interviews, a vendor will schedule face to face (or telephone) interviews with these participants in English over a video communication platform. Interviews will cover topics such as reasons for switching to B/F/TAF; experiences using CAB+RPV, including injection site reactions, side effects, time spent via clinic visits, etc; preferences for injectable and oral HIV medications; and treatment satisfaction post switch. Interviews will be recorded and transcribed for data analysis purposes. The qualitative interview will occur near the Week 4 visit (visit window range Week 3-9). Refer to [Appendix 11.4.2](#) for qualitative interview guide.

The qualitative interviewer would be responsible for notifying the investigator of all the AE's/SAE's/SSR's identified during the interview within 24 hours of awareness. Please refer to [Section 7.4](#) for the reporting process.

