### 11.3. Study Procedures Table

**Table 3. Study Procedures Table**

Study Procedures	Screening	Day 1 b	Week 4 c	Week 12 c	Week 24 c	30-Day Follow-up d	ESDD e	Notes
Informed Consent	X							
Medical History	X							
Concomitant Medications	X	X	X	X	X	X	X	At screening, concomitant medications taken within 30 days prior to screening will be recorded; at subsequent visits all medications since the last study visit will be recorded.
Adverse Events	X	X	X	X	X	X	X	
Complete Physical Examination	X							Complete physical examination (urogenital/anorectal examinations will be performed at the discretion of the investigator).
Symptom-Directed Physical Examination		X	X	X	X	X		Symptom-directed physical examination at all post-screening time points.
Vital Signs and Weight	X	X	X	X	X	X	X	
Height	X							
Urinalysis	X	X	X	X	X	X	X	
Urine Pregnancy		X	X	X	X	X	X	For participants of childbearing potential only
Serum Pregnancy	X							For participants of childbearing potential only
Chemistry Profile f	X	X	X	X	X	X	X	
Hematology Profile	X	X	X	X	X	X	X	CBC with differential and platelet count
CD4+ Cell Count	X	X		X	X		X	
Plasma HIV-1 RNA g	X	X	X	X	X	X	X	
HBV and HCV Serologies h	X							
Estimated GFR	X	X		X	X		X	Estimated GFR according to the Cockcroft-Gault formula for creatinine clearance
Metabolic Assessments i		X		X	X			
Baseline PK, Sparse PK: trough and postdose PK sample j		X	X	X	X			

Study Procedures	Screening	Day 1 b	Week 4 c	Week 12 c	Week 24 c	30-Day Follow-up d	ESDD e	Notes
Plasma Storage Sample		X	X	X	X		X	For optional future research
Whole Blood sample for potential HIV DNA genotyping		X						Whole blood sample for virology analysis
Plasma HIV-1 genotyping/phenotyping sample k			X	X	X		X	HIV-1 genotype/phenotype resistance testing for participants with unconfirmed virologic rebound with HIV-1 RNA value $\geq 200$ copies/mL
Dried Blood Spot (DBS) collection			X	X	X		X	TFV-DP from DBS will be run in retrospect for participants with confirmed viral failure.
HIVTSQs		X		X	X			
HIVTSc Questionnaire			X					
Additional study specific questions		X	X					
Qualitative interview			X					Qualitative interview will explore in-depth experiences on CAB+RPV, reasons for switch B/F/TAF and satisfaction post switch. The visit window for the interview is from Week 3 to Week 9.

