Study Drug Accountability		X	X	X	X	X	X	
Study Drug Dispensation		X		X				
Observed Dosing		X	X	X				Participants must take their study drug in the clinic for observed dosing on Day 1, Week 4, and Week 12.

CBC = complete blood count; CD4+ = clusters of differentiation 4; DNA = deoxyribonucleic acid; DBS = dried blood spot; ESDD = early study drug discontinuation; GFR = glomerular filtration rate calculated using the Cockcroft-Gault equation; HBV = hepatitis B virus; HCV = hepatitis C virus; HIV-1 = human immunodeficiency virus type 1; HIVTSQs = HIV treatment satisfaction status questionnaire [quantitative]; HIVTSQc = HIV treatment satisfaction change questionnaire [quantitative]; RNA = Ribonucleic acid; PK = pharmacokinetic(s); TFV-DP = tenofovir diphosphate.

- a Evaluations to be completed within 42 days prior to Day 1 visit.
- b Participants will be dispensed study drug at the Day 1 visit; initiation of treatment with the study drug must take place in the clinic for observed dosing at Day 1 visit.
- c All study visits are to be scheduled relative to the Day 1 visit date. Visit windows are  $\pm 2$  days of the protocol-specified date through Week 12,  $\pm 6$  days of the protocol-specified date for Week 24. For the purpose of scheduling a 30-day follow-up visit, a  $\pm 6$ -day window may be used. Those participants who prematurely discontinue study drug and continue in the study through at least one subsequent visit after the early study drug discontinuation visit will not be required to complete the 30-day follow-up visit.
- d Only applies to participants who miss the Week 24 visit, and must be completed within 30 days of discontinuing study drug.
- e Early study drug discontinuation visit to occur within 72 hours of last dose of study drug.
- f Chemistry profile: alkaline phosphatase, AST, ALT, total bilirubin, direct and indirect bilirubin, total protein, albumin, bicarbonate, BUN, calcium, chloride, creatinine, glucose, potassium, and sodium.
- g For any post-Day -1 visit, if the HIV-1 RNA value is  $\geq 50$  copies/mL, a retest should be performed at a scheduled or unscheduled visit 2-4 weeks after the date of the original test.

- h Hepatitis B virus surface Antigen (HBsAg), Hepatitis B core antibody (HBcAb), and Hepatitis C virus (HCV) serologies (reflex HCV RNA is performed in participants with positive HCV Ab serology)

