#### Discussion theme 1. Perspectives on HIV treatment overall

3. Please take a look at the images below. Which image do you think best matches how you feel about HIV treatment in general?

- a. How did you come up with that image?
- b. How does HIV treatment fit into your life?

4. What would your ideal HIV treatment look like?

- a. How would it be administered?
- b. How frequently would it be taken?

5. What are your thoughts about Biktarvy compared to Cabenuva?

- a. Does one have advantages over the other in any way?
- b. Do they differ in how they make you feel about your HIV?

Participant Interview Guide CAB+RPV switch study

Participant ID Number: \_\_\_\_\_ Date of Interview: (month/day/year) \_\_\_\_\_ Interviewer Initials: \_\_\_\_\_

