**Discussion theme 4. Biktarvy Treatment Experience and Perceptions**

17. Now let's talk about your decision to switch to Biktarvy. How did you learn about Biktarvy?
  - a. How did you hear about Biktarvy?
    - i. Who did you first hear about it from?
  - b. How was the treatment explained to you?
18. What factors contributed to your decision to start (or re-start) Biktarvy?
  - a. What factors led you to switch to Biktarvy?
  - b. What information did you use to make your decision?
  - c. Who did you talk with to help make your decision?
  - d. To what extent was your healthcare provider involved in your decision to start Biktarvy?
19. What expectations did you have of Biktarvy prior to starting?
  - a. Thinking back to before you switched to Biktarvy, do you feel that you were provided adequate information about the treatment?
  - b. Did you have any concerns before taking Biktarvy?
    - i. What did your provider do to address your concerns?
  - c. Is there any information that you wish you had known before starting Biktarvy?
20. Prior to starting Biktarvy following switching from Cabenuva, had you ever taken Biktarvy before?
21. What feelings have you had since starting (or re-starting) treatment with Biktarvy?
  - a. How does it feel to take Biktarvy?
    - i. Do you experience any issues taking Biktarvy?
  - b. How has your experience changed after your few doses?
    - i. Were there any changes that made taking Biktarvy easier? Any changes that made taking Biktarvy more difficult?
22. Overall, how do you feel about your treatment with Biktarvy?
  - a. Is there anything you like about taking Biktarvy?
23. How does Biktarvy compare to other HIV treatments you've received?
  - a. To what extent are you comfortable with the way Biktarvy treatment is given?
  - b. Does treatment with Biktarvy affect your quality of life? In what ways?
  - c. How does treatment with Biktarvy impact your outlook for the future?
24. Do you ever miss taking any doses of your HIV therapy on time? If yes, how often? Why?
  - a. What helps you to take Biktarvy on time?

Proprietary and Confidential | Page 7

Participant Interview Guide CAB+RPV switch study

Participant ID Number: \_\_\_\_\_ Date of Interview: (month/day/year) \_\_\_\_\_ Interviewer Initials: \_\_\_\_\_

25. So, we are coming to the end of our discussion. Is there anything else that you would like to share about your experience you're your HIV treatment experiences?

□□

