3.3. Examination of Participant Subgroups

Participants in North America (including USA and Canada) will have safety, efficacy, and sparse PK assessments, receive quantitative questionnaires, and be eligible for qualitative interviews, while participants in France will have safety and efficacy assessments and receive quantitative questionnaires. Since French participants did not undergo PK analysis, a subgroup analysis will be conducted on the demographic and baseline characteristics tables, to distinguish participants from North America sites vs. French sites. The groupings used in the final analysis are listed below.

Summary tables to be grouped by North America, France, and Total:

- Enrollment by country
- Participant disposition
- Important protocol deviation
- Demographics and baseline characteristics
- Duration of exposure to study drug (B/F/TAF)

- Adherence to study drug (B/F/TAF)
- Analysis sets
- Persistence with study drug (B/F/TAF)
- Post study antiretroviral medications.

Summary tables and figures to include participants from North America site only:

- Plasma BIC/CAB/RPV Concentrations.

Summary tables and/or figures to include participants from all sites as a Total group:

- HIV-1 RNA < 50 and \geq 50 copies/mL for D = F and M = E approach
- CD4 cell count and CD4 percentage
- Adverse events and deaths
- Laboratory evaluations: hematology, chemistry, metabolic assessment, and laboratory abnormalities
- Vital signs
- HIV Treatment Satisfaction Status (HIVTSQs) and HIV Treatment Satisfaction Change (HIVTSQc)
- Study-specific questionnaire on Day 1: questions related to participant experience with CAB + RPV
- Study-specific questionnaire on Week 4: questions related to participant experience after switching to oral B/F/TAF.

All available data for participants from North America (USA and Canada) and France will be included in the data listings.

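### The qualitative interview window opens about a week before the Week 4 HIVTSQc and neither document requires the form first, so some North American participants can discuss the switch before they score it.

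*Protocol*

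**What the plan says.** Protocol Section 2 lists one secondary endpoint for treatment satisfaction: "Change in HIV treatment satisfaction (HIVTSQc) score at Week 4". SAP 9.1 keeps that status and places the HIVTSQs under other endpoints.

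- **Form.** Protocol 6.5.1.2: "HIVTSQc is to be completed by the participant at Week 4". The Week 4 visit has a tolerance of plus or minus 2 "days of the protocol-specified date through Week 12" (Table 3, footnote c).
- **Interview.** Protocol 6.5.1.4 gives the window in the words "The qualitative interview will occur near the Week 4 visit (visit window range Week 3-9". The Table 3 note agrees: "The visit window for the interview is from Week 3 to Week 9". SAP 1.2.1 repeats it.
- **Content.** Protocol 6.5.1.4 lists reasons for switching, experience of CAB+RPV, preferences and satisfaction after the switch as interview topics. Question 5 of the guide asks: "What are your thoughts about Biktarvy compared to Cabenuva".
- **Who.** Interviews are in English, for consenting participants in North America. French participants complete the questionnaires but are not interviewed (Protocol 3.1 and 4.1).
- **Analysis.** SAP 3.3 places the HIVTSQc under "Summary tables and/or figures to include participants from all sites as a Total group". SAP Table 3-4 gives the HIVTSQc and the interview one shared analysis window, Day 2 to Day 56, with no order between them.

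**The concern.** The HIVTSQc asks the participant to compare the new treatment with the old one. The interview spends up to an hour on the same comparison. If it comes first, the answers on the form may partly reflect that conversation. The study is open-label and single-arm, so no control group shares the same measurement sequence. No planned summary separates participants who were interviewed before the form from those who were not. The pooled total would mix the two, and a reader could not tell whether order played a part.

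**Working it through.** The plan states no figure on this point, so there is nothing to reproduce. The check is calendar arithmetic plus a comparison of the relevant passages.

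**Inputs**
- Interview window: Week 3 to Week 9, taken as Day 21 to Day 63, which is 63 − 21 + 1 = 43 days (Protocol 6.5.1.4 and Table 3; conversion to days is mine).
- HIVTSQc: nominal Day 28 (SAP Table 3-4), plus or minus 2 days, so Day 26 to Day 30.
- Participants: about 35 planned, about 10 of them in France, leaving about 25 who could be interviewed (Protocol 4.1).

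**How far ahead the interview can fall.** Lead time = visit day − 21. Expected number interviewed first = 25 × lead time / 43, assuming even scheduling and that all 25 are interviewed.

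| Week 4 visit on | Lead time | Share of window | Expected number of 25 | Share of 35 |
|---|---|---|---|---|
| Day 26 | 5 days | 5/43 = 11.6% | 2.9 | 8.3% |
| Day 28 | 7 days | 7/43 = 16.3% | 4.1 | 11.6% |
| Day 30 | 9 days | 9/43 = 20.9% | 5.2 | 15.0% |

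The ceiling is all 25, or 25/35 = 71%, because no rule prevents it. Even scheduling is only an assumption. The aim of interviewing near Week 4 could raise the count; separate consent and the English-only restriction would lower it.

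**Is there an ordering rule?** Protocol 6.5.1.2, 6.5.1.4 and Table 3, and SAP 1.2.1, 3.7.2 and 9.2.1, contain none. The SAP window is also wider than the visit window: a form completed late, up to Day 56, still counts as Week 4, so in the analysis the lead could exceed 9 days.

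**Are the interview probes balanced?** The items, side by side:
- Question 14 (Cabenuva) probes both likes and dislikes. Question 22 (Biktarvy) has only "Is there anything you like about taking Biktarvy".
- Question 8c prompts on injection feel, visit frequency and side effects of Cabenuva. Question 19c has no such list for Biktarvy.
- Against that, question 21 asks about issues and difficulties with Biktarvy, question 19b about concerns before starting it, and question 16a what would have kept the participant on Cabenuva. Question 5 is neutral.

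The imbalance is real but confined to the first two pairs.

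**What cannot be computed.** The pooled mean would move by the share interviewed first, times the average effect of a prior interview on the score. The documents give nothing on that effect, so no shift in points is offered.

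**The case against.** The strongest reply is that the effect is speculative and small. The study is descriptive, with no formal testing (SAP 3.4) and no decision threshold for this score. Everyone, including the French participants, completes a Day 1 survey that lists Cabenuva side effects and 17 named reasons for switching and asks for the top one, so some rehearsal is common to all. The HIVTSQs also gives a Day 1 baseline that precedes every interview. Dates exist to recover the order: the guide has an interview-date field, and analysis windows are assigned by study day.

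Much of this stands. Any effect of the interview is an increment over the Day 1 survey, and its size is unknown. Recoverable dates help only if someone uses them, and no planned summary does. The HIVTSQs at Weeks 12 and 24 comes after the whole interview window, so it is not free of a prior interview either, and it is not the secondary endpoint.

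A reader might also infer that the guide is slanted throughout and pushes the score towards the sponsor's drug. The documents do not support that. The imbalance is limited to question 22 against 14 and question 19c against 8c, other items cut the opposite way, and the guide tells interviewers not to use it as a verbatim script.

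One objection changes the remedy. SAP 2.1 reports the North American interim in the past tense, after every North American participant had completed Week 12 or stopped study drug. The interviews are therefore in the past, and a protocol change alone would come too late for them.

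**Conclusion.** The point holds as an ordering gap. The interview can precede the once-only HIVTSQc by up to 5 to 9 days within the protocol's windows, neither document prevents it, and the analysis pools those forms with forms from participants who were never interviewed. With even scheduling and at most 25 interviewees, about 3 to 5 participants are affected (8% to 15% of 35); the unprotected ceiling is 25.

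It does not follow that the HIVTSQc result is biased by a known amount or in a known direction. A reader might infer an inflated satisfaction score, but nothing in the documents gives the size or sign of an order effect. The matter concerns one secondary, descriptive endpoint; it does not touch the co-primary safety endpoints. It merits correction because the remedy is cheap and the order would otherwise go unreported.

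**What to change.** **Protocol.** In 6.5.1.4 and the Table 3 note, open the interview window only once the Week 4 HIVTSQc has been completed, and keep Week 9 as its end. No interview day would then precede the form. The cost is about one week of window (5 to 9 days); 63 − 30 = 33 to 63 − 26 = 37 days remain. No visit or procedure is added.

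**SAP, for data already collected.** Leave the description of conduct in 1.2.1 as it is, since it records what was done. Add to 9.2.1 a flag for HIVTSQc forms completed on or after the interview date, so that same-day cases are included, and summarise the HIVTSQc total with and without the flagged forms. This costs one derived variable and one extra summary. With so few forms likely to be flagged, the comparison would show how many participants are involved and whether the summary changes; it could not estimate an order effect with any precision.
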